11.4 Original Power analysis and sample size calculation

Assumptions for the initial sample size calculation were:

- 1) Rate of development of CNS atrophy in early PP-MS patients is equivalent, or greater than the rate of development of brain atrophy in RR-MS patients and similar to rate of development of brain atrophy in SP-MS patients (Fox, Jenkins et al. 2000)
- 2) Rate of development of brain atrophy in PP-MS patients varies considerably between individuals, ranging from +1.8%/year to -3.6%/year (Mean -1.03%, SD 1.3%) for BPF and from +1.7%/year to -4.2%/year (Mean -1.50%, SD 1.6%) for grey matter fraction (Sastre-Garriga, Ingle et al. 2005)
- 3) Within 5 years of follow-up, the rate of development of brain atrophy, ventricular atrophy, cervical cord atrophy and the rate of accumulation of T2LV and T1LV seem to be significantly more stable intra-individually than inter-individually (Ingle, Stevenson et al. 2003), although the intra-individual coefficient of variation values are not provided in this publication
- 4) Due to these inter-individual differences in the rate of accumulation of brain atrophy, the reported sample size estimates in SP-MS patients utilizing changes in brain atrophy detected by SIENA methodology applied to 1.5T MRI scans, indicates that to detect 50% therapeutic effect in a therapeutic trial of 2 year duration with 80% power and 5% significance, the minimum number of subjects is 33 per arm (Altmann, Jasperse et al. 2008). The relevant data from this recent publication using SIENA methodology for calculation of whole brain atrophy in SP-MS

patients by Altmann, Jasperse et al. are summarized in the table below (selected conditions for current trial are highlighted):

Duration of Therapy	Expected therapeutic effect:	90% power			80% power		
		30% Th effect	40% Th effect	50% Th effect	30% Th effect	40% Th effect	50% Th effect
1 year	Min# subj/arm	212	120	77	158	89	57
2 years	Min# subj/arm	123	69	45	92	52	33
3 years	Min# subj/arm	107	60	39	80	45	29

Collecting at least 12 months of pre-treatment baseline volumetric MRI data (i.e. rate of development of brain atrophy, gray matter atrophy, ventricular enlargement and spinal cord atrophy) and clinical data will allow us to calculate individualized rates of CNS tissue destruction and disability progression. Based on the data described under 1)-3), employing such individualized rates of development of CNS tissue destruction for the determination of therapeutic effect between active drug and placebo is expected to significantly increase the power for detection of group differences, effectively decreasing the number of subjects necessary for demonstrating therapeutic efficacy of an experimental neuroprotective therapy (Figure 2). Additionally, employing more sensitive methodology (3T magnet strength) and novel analyses (e.g. volumetric analysis of entire cervical spinal cord) may further increase power for detection of group differences.

However, NDU did not have any longitudinal data on a PP-MS cohort that could be utilized for exact sample size analysis and the only longitudinal data that were published at the inception of this trial and could be utilized for sample size calculation were those based on whole brain atrophy as detected by SIENA methodology. Therefore, we used published sample size estimates for the SP-MS patients (Altmann, Jasperse et al. 2008) and targeted patient accrual to reach 66 treated patients (33 per arm).

In 2016 we performed and published pre-determined analysis of the 58 outcome measures (see section 11.5) collected in 1 year pre-treatment baseline period on first ≥ 30 IPPOMS patients and validated our findings in the 2 validation cohorts consisting of 34 remaining IPPOMS patients and 29 SP-MS patients from RIVITALISE trial (Kosa, Ghazali et al. 2016). This analysis demonstrated that above-stated assumptions were incorrect, that brain atrophy measured by SIENA technology was no more sensitive than clinical outcomes. Instead, based on this pre-defined analysis we selected CombiWISE as primary outcome and brain ventricular atrophy measured by LesionTOADS methodology as secondary outcome.

11.5 Selection of primary outcome measure

Based on the analysis of data from pre-randomization baseline period for the first 30 patients

Based on higher resolution of 3T versus 1.5T MRI scans and some indication from studies, either published or reported at conferences, that show that alternative measures, such as e.g. gray matter atrophy or MRS may be more sensitive than whole brain atrophy in detecting CNS tissue damage longitudinally (Fisher, Lee et al. 2008), we will employ an adaptive trial design that will allow us to

select most robust (i.e. most sensitive and most accurate) primary outcome measure for the final analysis.

Specifically, we will analyze MRI and clinical/paraclinical quantitative data when 30 patients reach month 0 (i.e. will complete pre-randomization baseline period)(Kosa, Ghazali et al. 2016). From this analysis we will calculate the rate of progression of CNS tissue destruction as assessed by MRI and clinical biomarkers defined in Section 10.2, for individual patients and for the entire cohort. Because SIENA methodology for detection of progression of brain atrophy, which is currently utilized as the default primary outcome measure, calculates progression of brain atrophy as a %-age of baseline brain tissue, we will perform the same type of analysis for every other defined outcome; i.e. we will quantify the biomarker at month -12 (baseline) and months -6 and 0 and will express the values measured at months -6 and 0 as a %-age of the baseline value (i.e. assigning 100% to the value measured at month -12). For the 1st level of analysis, we will compare all outcome measures based on the measurements collected at month 0 (see Figure 4A for explanation). For each biomarker (i.e. outcome measure) we will calculate the z-score as the average change from baseline divided by the standard deviation (SD). Biomarkers with the most robust change from baseline and lowest spread of values will have the highest z-score. Figure 4A shows 3 hypothetical biomarkers: Biomarker 1 has on average the lowest magnitude of change from baseline (i.e. low sensitivity) and relatively high spread (i.e. low accuracy), leading to the lowest z-score. Biomarker 2 has the most robust change from baseline (i.e. high sensitivity), but also the widest spread of values (i.e. lowest accuracy), resulting in low z-score. Biomarker 3 has an intermediate change from baseline (i.e. intermediate sensitivity) but very low spread of values (i.e. high accuracy), resulting in the highest z-score. Biomarker 3 would be selected as the primary outcome measure.

[figure not shown]

Figure 4:

A/ First level of comparative analysis: all outcome measures will be expressed as %-age of baseline values for all 30 patients. We will calculate z-scores for all outcome measures as Average (30 changes from baseline)/SD and select the biomarker with largest z-score as primary outcome measure.

B/ Second level of comparative analysis: if two biomarkers had identical or very similar z-scores in the first level of analysis, we would evaluate z-scores based on data collected at -6 months using identical methodology.

If we encounter a situation in which two or several biomarkers have identical or very similar z-scores in the first level of analysis, we will then evaluate these biomarkers based on data collected at month -6 (i.e. at Mo -6; Figure 4B).

The logic of choosing to compare z-scores rather than the simpler selection of the biomarker giving the most robust difference from baseline is as follows: the absolute difference of the longitudinal measurements of a biomarker from its baseline value is the combination of biological progression of the disease and of any technical inaccuracy of measurement. From the biological standpoint, PP-MS is a progressive disease – patients may have periods of stabilization, but in contrast to RR-MS, there are no periods of improvement. Therefore, if in some patients we measure improvement from baseline, we can assume this is most likely due to technical inaccuracy of measurement, than due to the biology of this disease. Because technical errors should be random (i.e. may result in apparent improvements as much as in exaggerated progression) a greater spread of biomarker values between patients would likely reflect greater technical measurement errors. Therefore, using standard deviation as a denominator will ensure selection of an outcome measure that combines the greatest sensitivity for detecting CNS tissue destruction and the greatest accuracy of measurement.

If, based on this analysis, we identify an outcome measure that is more sensitive and more precise than whole brain atrophy measured by SIENA methodology, we will select this new measure as the primary outcome measure.

This analysis was performed and published, including measurements of z-scores (*Kosa, Ghazali et al. 2016*). We have compared total of 58 clinical, imaging, electrophysiological and optical coherence tomography outcomes. In the first IPPOMS cohort (which ended up being 35 patients because we lost some MRI outcomes due to technical issues such as poor quality of scans and the protocol stipulated minimum of 30 patients per outcome) we observed that total of 15 outcomes reached statistical significance based on un-adjusted p-values (See Table 2 in the (*Kosa, Ghazali et al. 2016*)). We then validated these 15 outcomes for their ability to reliably detect yearly MS disease progression in 2 independent validation cohorts: IPPOMS2 cohort (n=34) and RIVITALISE cohort (n=29). Seven out of 15 outcomes validated statistically-significant change in both independent validation cohorts, when properly adjusting for multiple comparisons. Surprisingly, the default primary outcome for IPPOMS protocol, brain atrophy measured by SIENA methodology was not validated. While six MRI biomarkers (ventricular volume and 5 diffusion-tensor imaging [DTI] markers) validated statistically-significant change in both validation cohorts, our enthusiasm for these outcomes was lowered by observation that only one of them, ventricular atrophy, showed any correlation with clinical outcomes. This measure had mild correlation with 2 cognitive scales (PASAT and SDMT) and with a MS functional composite (MSFC) scale. However, this correlation was observed only in the cross-sectional paradigm, which benefited from a broad range of disabilities present in merged untreated progressive MS cohort (n=98). In contrast, we observed absolutely no correlation between any MRI outcome and any clinical measure in 1-year longitudinal paradigm – in other words, change on MRI biomarkers did not correlate with change in any clinical outcome. The article explains in length why this is so, documenting poor signal-to-noise ratio (SNR) of even best performing MRI biomarkers for the level of change observed in the 1-year longitudinal MS data in comparison to scan-re-scan variability observed in MRI technical controls (i.e. healthy donors scanned twice at each scanner).

Because of this we concluded that MRI outcomes utilized in small Phase II trial will be unlikely to predict change on clinical outcome (used for Phase III trial), which is a definition of a “surrogacy”. Therefore, we sought alternative outcome. We noticed that clinical scales were much better correlated, even though they too had relatively low SNR. One way to decrease the noise of the measurement is to use repeated measure analysis. Therefore, we hypothesized that to the degree to

which clinical scales reflect overlapping biology (i.e. measure overlapping neurological disability) to that degree they represent repeated measure analysis. Thus, rationally combining clinical scales would allow us to differentiate between disability caused by a structural lesion (which would affect multiple clinical scales congruently) from the performance noise, which would have random distribution among clinical scales. We have tested this hypothesis by designing Combinatorial Weight-Adjusted Neurological Clinical Scale (CombiWISE version 1), where we selected contributing clinical scales and adjusted their “weights” in final formula proportionally to z-scores (defined in the IPPOMS protocol and measured in the first [IPPOMS1] cohort). After we validated that CombiWISE v1 outperforms all other clinical and MRI biomarkers, we used statistical learning based on random permutations of the modeling cohort, to mathematically optimize CombiWISE outcome (Kosa, Ghazali et al. 2016).

Not only mathematically-optimized CombiWISE outperformed all remaining 57 studied outcomes, but it also retained highly statistically significant correlations with majority of clinical outcomes, including EDSS that is currently used for regulatory approval of MS drugs. However, in comparison to EDSS, which is ordinal scale from 0-10, CombiWISE is a continuous scale from 0-100. One point change in EDSS corresponds on average to 7.50 point change in CombiWISE with a standard error of 0.10, making CombiWISE significantly more sensitive (and specific) measure of neurological disability (Kosa, Ghazali et al. 2016).

11.6 Accrual number request

Up to 85 subjects are planned to be recruited based on current sample size calculation, to account for 20% drop-out and final number of treated subjects 33 per arm (66 total). These recruitment numbers were already achieved and interim analysis of the outcomes showed enhanced, rather than diminished power of new primary outcome (CombiWISE) in comparison to original default primary outcome (Brain atrophy measured by SIENA).

11.7 New power analysis

If the above-described analysis of secondary outcome measures identifies a new primary outcome, we will conduct a new power analysis for the selected new primary outcome, using two-sample t-test with estimates of mean and standard deviation of changes from baseline collected on the first 30 enrolled patients. Based on this new power analysis, we will amend the protocol to indicate the final accrual number request.

The new power analysis for CombiWISE, EDSS and ventricular volume change has been published for both within-group and between-group designs (Kosa, Ghazali et al. 2016). Using absolute change in the CombiWISE AUC outcome determined from the pre-treatment baseline data in IPPOMS cohort, following power calculation for AUC was derived:

Drug effect	untreated	treated	difference	Actual Power	N Pairs	Distribution	Normal
50%	51.24	25.62	25.62	0.807	28	Method	Exact
45%	51.24	28.18	23.06	0.806	34	Number of Sides	2
40%	51.24	30.75	20.50	0.802	42	Standard Deviation	46.2
35%	51.24	33.31	17.94	0.807	55	Correlation	0.5

30%	51.24	35.87	15.37	0.801	73	Nominal Power	0.8
25%	51.24	38.43	12.81	0.804	105	Null Difference	0
20%	51.24	40.99	10.25	0.802	162	Alpha	0.05

This demonstrates that substituting default primary outcome (Brain atrophy measured by SIENA (*Altmann, Jasperse et al. 2008*)) with CombiWISE primary outcome will significantly enhance power of the IPPoMS trial from estimated 80% of power to detect at least 50% drug effect to more than 80% power to detect at least 40% drug effect. Additionally, while brain atrophy measured by SIENA does not correlate with clinical outcomes, CombiWISE has strong, highly significant correlations with EDSS, which is used for regulatory approval of MS treatments, both in cross-sectional and longitudinal paradigms (i.e. yearly change in CombiWISE correlated with yearly change in EDSS). Therefore, CombiWISE can predict efficacy on EDSS outcome, but does so in considerably smaller cohorts and/or trials of shorter duration (*Kosa, Ghazali et al. 2016*).

12. HUMAN SUBJECT PROTECTION

12.1 Subject selection

The investigational nature and objectives of this trial, the procedures and treatments involved, as well as the attendant risks, discomforts, and potential benefits will be carefully explained to the patient. A signed consent form will be obtained by the principal investigator or an associate investigator. It will be carefully explained to patients that they may withdraw from the study at any time, for any reason.

All adult PP-MS patients fulfilling all inclusion criteria and for whom none of the exclusion criteria are applicable, irrespective of gender or race are included in the trial. The age limits are 18-65 years, inclusive. The rationale for this age limit is explained in detail under Section 4.7. The upper age limitation is scientifically justified in this very early stage of clinical trial; if idebenone proves its therapeutic efficacy in this optimally selected patient population, further studies will be required to determine the exact age limit of its efficacy in this disorder. This will permit to use more equitable populations in later phases of clinical development of idebenone for PP-MS.

12.2 Justification for exclusion of children

Patients under the age of 18 are excluded since the incidence of MS in this age group is extremely low and PP-MS is virtually non-existent. Consequently, insufficient numbers of patients in that age range would be available to provide reliable data.

12.3 Study safeguards

Because the effects of idebenone therapy on pregnancy and breastfeeding are unknown, patients able to become pregnant or able to father a child will be required to use appropriate methods of contraception for the trial duration and all women able to become pregnant will be evaluated with a pregnancy test every 6 months and before any MRI. Women over age 55 who have not had a period for one year will be considered menopausal and will not need pregnancy testing or contraception.

Women under the age of 55 will undergo pregnancy testing and will be required to use appropriate methods of contraception for the trial duration, unless there is a history of surgical menopause.

13. BENEFITS

13.1 Direct Benefit

Participants may receive direct therapeutic benefit from participation in this study

13.2 Indirect Benefit

The study will yield generalizable knowledge about the drug and disease state and will aid in developing future neuroprotective therapeutic trials in MS patients

14. SUMMARY/CLASSIFICATION OF RISK:

For the study as a whole

The risk is classified as more than minimal risk.

This is a reasonable risk in relation to the anticipated potential therapeutic benefit in a patient population for which there are currently no therapeutic agents with proven benefit and for obtaining generalizable knowledge that will facilitate more rapid screening of novel neuroprotective agents in low-inflammatory progressive MS subtypes.

15. CONSENT DOCUMENTS AND PROCESS

Prior to any testing under this protocol, including screening or pre-treatment tests and evaluations, written informed consent will be obtained from the subject in accordance with local practice and regulations. Study investigators will obtain informed consent, as noted in the Qualifications of Investigators section.

The background of the proposed study and the benefits and risks of the procedures and study will be explained to the subject. A copy of the informed consent document signed and dated by the subject will be given to the subject. Confirmation of a subject's informed consent will also be documented in the subject's medical records prior to any testing under this protocol, including screening or pre-treatment tests and evaluations.

On occasion, it may be necessary to obtain informed written consent by a phone discussion process. It may be necessary, for example if a participant has completed screening under protocol 09-N-0032, and has met all inclusion criteria except the washout period from a previous treatment. In some cases, waiting for completion of the washout phase may result in their being too old to enroll in this study. As most of our participants are traveled from other states, it is impractical to fly participants back to NIH solely for the consent process. For telephone/written consent, the following process will be followed.

This study and its consent form will be reviewed with the participant in person at their 09-N-0032 screening visits. Their questions will be answered. If they are interested in participating, they will be provided with an unsigned copy of the consent form to take home with them, or a copy will be mailed to them with a postage paid addressed return envelope. Once they meet all eligibility criteria (including completion of a washout period if needed), they will be contacted by telephone by someone authorized to obtain consent for the study. They will be asked to have a witness with them at the time of the telephone call. The consent form information will be reviewed again over the

phone and any further questions answered. If they agree to participate, the patient will sign and date the consent form, and have a witness sign and date the consent form. They will return the signed consent form to NIH. After the investigator who obtained consent signs the consent form, a complete signed copy will be sent to the participant. The original, signed consent form will be sent to medical records and an additional copy maintained in research records. The consent process will be documented in the medical and research records.

Information that is gained through this study will be available to the participating patients.

Consent forms are attached.

16. DATA AND SAFETY MONITORING

16.1 Monitoring plan for the study as a whole

This study will be monitored by a Data and Safety Monitoring Board (DSMB). [name] [name] is a board-certified neurologist with full clinical privileges. She will serve as the Independent Medical Monitor. [name] is independent of NIB and will be involved in crucial decision making regarding clinical issues that may arise during this trial. We are instituting an NIB independent medical monitor as a way to mitigate [name] conflict of interest (COI). [name], the PI on the study, is co-inventor on an NIH patent related to the use of idebenone and as such will receive patent royalty payments.

16.2.4 Role of DSMB

- a. Monitor/review AE on yearly basis and SAE within 15 days of receiving the SAE report.

16.2.5 Proposed meeting frequency/ schedule

The DSMB will meet on a yearly basis via teleconference. Yearly AE data and clinical data will be collected and provided to the DSMB for review. Additionally, all SAEs will be communicated to the DSMB within 7 days of occurrence.

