9.2.19 Definition of Serious Adverse Event (SAE)

A serious adverse event is any untoward medical occurrence or effect at any dose, that:

- results in death,
- is life threatening,
- results in persistent or significant disability/incapacity,
- requires in-patient hospitalization[‡] or prolongation of existing hospitalization,
- results in cancer,
- is a congenital anomaly/birth defect in the offspring of a study subject,
- is deemed, by the investigator, an important or serious medical event that may jeopardize the patient or may require intervention to prevent one of the other outcomes listed above should be considered serious (i.e., intensive treatment in an emergency room or at home for allergic bronchospasm; blood dyscrasias or convulsions that do not result in hospitalization; or development of drug dependency or drug abuse.)

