1.2 Criteria for individual subject withdrawal

A subject *must* permanently discontinue study drug treatment for any of the following reasons:

1. The subject becomes pregnant (pregnancy test will be performed for female patients with child bearing potential during study visits as indicated in section 7.5.6). If a patient becomes pregnant, treatment must be *immediately* discontinued. The pregnancy must be reported to the NIB (treating physician/research nurse) and to the IRB immediately. Information about the subject, the subject's pregnancy, the outcome of the pregnancy, and the status of the infant at 8 to 12 weeks of age will also be collected.
2. The subject desires to discontinue study drug treatment under this protocol. Patients have the right to withdraw from the study at any time and for any reason. The investigator also has the right to withdraw patients from the study in the event of an intercurrent illness, adverse events, treatment failure, protocol violations, administrative reasons, or other reasons.
3. 1st MS safety criterion: Worsening of more than two points on the EDSS scale (*Kurtzke 1983*) compared to baseline, confirmed one month later on an extra follow-up visit. The treatment will be discontinued, but the patient will be followed off therapy to collect all predetermined outcome measures as per "intention to treat" analysis.
4. 2nd MS safety criterion: The average number of new CEL (which represents a measure of MS-related brain inflammatory activity) increases after initiation of idebenone therapy 3 standard deviations above the average number of CEL during pre-treatment baseline or for patients with no CEL observed on MRIs collected during baseline period (expected to be majority of PP-MS patients), the number of CEL recorded on a single follow-up MRI reaches 10 CEL (total). Treatment will be discontinued, but the patient will be followed off therapy to collect all predetermined outcome measures as per "intention to treat" analysis.
5. Laboratory safety criteria: ALT (SGPT) or AST (SGOT) more than three times the upper limit of normal during regular laboratory monitoring and remains more than three times the upper limit after one week of cessation of idebenone dosing. Any other highly abnormal laboratory finding that is deemed critical by an investigator and that persists for 1 week after cessation of drug dosing.

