1.3 Criteria for stopping the study

All SAEs will be communicated to the DSMB. Depending on the nature of the SAE and its potential relationship to the study medication, the DSMB may request unblinding of the treatment allocation for any patient that suffers SAE(s) and will decide on further action.

17. Quality Assurance (QA)

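### Between yearly DSMB meetings, a mandatory safety stop of study drug that is not classed as an SAE (chiefly a persistent ALT/AST elevation) has no stated route to the DSMB and can wait up to about 12 months

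*Protocol*

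**What the plan says.** Three short subsections of the protocol set the flow of safety information to the DSMB.

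- **Role (16.2.4):** "Monitor/review AE on yearly basis and SAE within 15 days of receiving the SAE report".
- **Schedule (16.2.5):** one teleconference a year, for which "Yearly AE data and clinical data will be collected and provided to the DSMB for review". The only faster item is the SAE: "Additionally, all SAEs will be communicated to the DSMB within 7 days of occurrence".
- **Stopping (16.3 in the contents list, printed as 1.3):** after an SAE, "the DSMB may request unblinding of the treatment allocation for any patient that suffers SAE(s) and will decide on further action". No other event is named there.

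The withdrawal section (9.3 in the contents list, printed as 1.2) makes permanent discontinuation mandatory for five reasons. Three are safety criteria:

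- **Item 3:** "1st MS safety criterion: Worsening of more than two points on the EDSS scale", confirmed at an extra visit one month later.
- **Item 4:** a rise in contrast-enhancing lesions of 3 SD over the pre-treatment average or, for patients with none at baseline, when "the number of CEL recorded on a single follow-up MRI reaches 10 CEL (total".
- **Item 5:** "ALT (SGPT) or AST (SGOT) more than three times the upper limit of normal during regular laboratory monitoring", still present one week after dosing stops, or another laboratory finding that the investigator deems critical and that persists for a week off drug.

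The section requires the reason for the stop to be recorded in the patient's file and the patient to be followed. It does not mention the DSMB. Section 9.1.16 does so for one kind of stop, pregnancy: the patient's assignment is then disclosed to the investigators and the DSMB.

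**The concern.** Safety over 24 months is the first primary goal (Protocol 5.2), and SAP 4.1 lists premature discontinuation of study treatment among the primary safety endpoints. Protocol 7.6.10 names the DSMB as the body that may end the trial early over safety. Section 8.1 says that the drug's effect on dysregulated immune responses in humans is unknown and hard to predict.

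Items 3 to 5 are the events that the protocol itself judged serious enough to end dosing for good. Yet the fast channel depends on whether an event is classed as an SAE, not on whether it forced a stop. A stop that falls outside the SAE definition joins the routine yearly package. The DSMB has discretion over what to do about a safety signal, but between meetings it cannot use that discretion on an event it has not been told about.

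**Working it through.** There is no power or error-rate figure to reproduce. The check is to trace each route to the DSMB and then compare delays.

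**1. Which item 3 to 5 stops already have the 7-day route?** None of the three criteria is in itself an SAE, so classification depends on 9.2.18 and 9.2.19.

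| Criterion | SAE route | What is left |
|---|---|---|
| Item 3, EDSS | A confirmed loss of more than two points will often meet the limb "results in persistent or significant disability/incapacity"; 9.2.18 also marks Grade 4 (life-threatening or disabling) events as SAEs | The occasional stop judged non-serious |
| Item 4, lesions | A lesion count on MRI meets no automatic limb; investigator judgment could make it an important medical event | A non-SAE stop is possible but should be rare: after the first NIH MRI, contrast is given on clinical judgment, and 7.5.3 reports true enhancing lesions as extremely rare at baseline with no increase on treatment |
| Item 5, ALT/AST | A persistent, asymptomatic elevation meets no automatic limb | The main residue |
| Item 5, other laboratory | A finding deemed critical is close to the investigator-judged important-medical-event limb | Little |

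**2. Does another route carry the residue to the DSMB?**

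- Adverse Event Form (9.1.16) and patient file (9.3): records only.
- Independent Medical Monitor (16.1): involved in crucial clinical decisions, but with no event list and no stated duty to inform the DSMB.
- IRB and CD (section 18): non-serious events are reported within 14 days only if they are unanticipated problems, and the DSMB is not the recipient.
- Code release by the pharmacy (7.4): on DSMB request, so the DSMB must already know of the event.
- Pregnancy disclosure (9.1.16): a real exception to SAE-only notice, but outside items 3 to 5.

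The subsection that the contents page labels as the list of DSMB members was not available for this review. The role, schedule and stopping subsections were, and they contain no further notice duty.

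**3. Delay to DSMB notice.**

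- SAE: 7 days.
- Non-SAE stop under items 3 to 5: until the next yearly meeting, at most about 365 days. If the stop falls at a random time between meetings (an assumption), the mean is 365/2 = 182.5 days.
- Difference: 365 − 7 = 358 days at most; 182.5 − 7 = 175.5 days on average.
- The maximum is 12/24 = half of the treatment period.

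**4. Frequency.** The protocol gives no rate for any of items 3 to 5 and no split into SAE and non-SAE stops. The nearest figure, in 8.1, is a frequency between 1/1000 and 1/100 for changes in hepatic laboratory values in earlier trials, mainly in Alzheimer's dementia. It does not transfer. It counts any hepatic change, not a persistent threefold elevation. The Alzheimer's trials described in section 4.5 used at most 360 mg three times daily (3 × 360 = 1080 mg/day), against 2250 mg/day here. It also says nothing about items 3 and 4. The chance of a delayed notice, or of a cluster of them, therefore cannot be computed from the documents.

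**The case against.** The strongest reply is that rapid SAE reporting plus yearly review of the rest is a coherent two-tier plan. Most of the serious events behind these stops would already be SAEs. The Medical Monitor and the IRB/CD route give some independent oversight between meetings, nothing bars ad hoc contact with the DSMB, and the known safety profile makes a cluster unlikely. Moreover, 7.6.10 of this version states that the data analysis is complete and that idebenone was safe and well tolerated, so a new reporting rule would help no participant in this trial.

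Much of this stands. It narrows the gap and keeps the severity low. It does not supply a DSMB notice for a persistent ALT/AST stop, and a permission to make contact is not a duty to do so.

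A reader might infer more than the documents support, in four ways:

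- *Only SAEs reach the DSMB between meetings.* Not so: pregnancy stops do too.
- *Items 3, 4 and 5 are equally exposed.* Step 1 of the working shows that the exposure lies mainly in ALT/AST.
- *There is a calculable probability that the DSMB would miss a cluster.* Any such figure would rest on assumed stop rates and would count all stops, including those that reach the DSMB as SAEs.
- *Patients are left unprotected.* They are not. Dosing ends, adverse events that led to the stop are followed until resolved or stable, item 3 and 4 patients continue outcome assessments off drug, and scheduled liver tests (every 3 months in year 1, every 6 months in year 2) screen everyone else.

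**Conclusion.** The point holds in a limited form. Pregnancy apart, the protocol requires only SAEs to be sent to the DSMB between its yearly meetings. A permanent stop under a 9.3 safety criterion that is not classed as an SAE can therefore wait up to about 12 months for DSMB notice, about 358 days longer than an SAE. The stops affected are chiefly persistent ALT/AST elevations and, rarely, an item 4 stop or an item 3 stop judged non-serious.

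The 12-month figure assumes meetings a full year apart and no voluntary contact in between. It is a worst case for notice to the DSMB, not for all independent oversight. Confidence is high that the text has no such duty; frequency and consequence are unknown. There is no effect on the efficacy inference. Leaving the response to DSMB judgment, without a numerical stopping rule, is legitimate and is not criticised here. Severity is low: a cheap improvement, now useful mainly for the record and for reuse of this design.

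**What to change.** Add one sentence to Protocol 16.2.5 and cross-refer to it in 16.3:

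> Each permanent discontinuation of study drug under 9.3 items 3-5, whether or not classed as an SAE, will be communicated without treatment allocation to the DSMB and the Independent Medical Monitor within 7 days; the DSMB decides on any further action.

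This applies the existing 7-day SAE timeline and avoids any dispute over seriousness. Withdrawal rules, blinding, sample size, type I error and DSMB discretion are unchanged.

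The cost is a few extra notices. With 66 treated patients and assumed whole-trial stop rates of 0.1%, 1% and 5% per patient, the expected numbers are 66 × 0.001 = 0.07, 66 × 0.01 = 0.66 and 66 × 0.05 = 3.3. At each assumed rate this is a ceiling on new notices, because stops that are SAEs are already sent.
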